Your clinical trial gynecologist and their medical assistants will perform a standard of care routine gynecologic examination of the external genitalia and vagina. In order to establish an objective baseline of vestibular appearance, a visual inspection will be documented, including presence or absence of erythema. In order, to further establish the post-menopausal, non -estrogenized state of the vagina, testing of the vaginal pH as well as superficial smears of the lateral vaginal wall will be taken to determine vaginal maturation index, as is the standard of care. To document localization of areas of significant/severe pain in the vulvar vestibule, a standard of care, Q-tip test will be performed. The Q-tip test involves palpating the vulvar vestibule with a soft, cotton wool-tipped stick and noting both location and intensity of any pain. These procedures are standard of care. None of these procedures are experimental.

Industry standard questionnaires will be administered to subjects at the initial screening and each of the three subsequent study clinic visits. These include the following industry standard, well established in the literature, questionnaires: Female Sexual Function Index (FSFI) Wiegel M et al J. Sex Marital Ther. 2005; 31: 1-20, Vulvovaginal Symptoms Questionnaire (VVSQ) Erekson et al, Menopause 2013 September: 20(9): 973-979, Sexual Distress Scale-Revised (SDS-R) DeRogatis L, et al J. Sex Med. 2008: 5: 37-364., In addition, the subjects will be asked to keep a weekly diary documenting their pain on a 0- 10 point Numerical Rating Scale (NRS) of pain intensity where (0) is no pain; (1-3) is mild pain; (4-6) is moderate pain (7-9) is significant pain and (10) is severe pain, and to fill out the industry well established in the literature questionnaire: Sexual Activities Log (SAL) DeRogatis, L R, et al. J. Sex Med 2009;6:175-183 in order to document that they are sexually active and the impact that the study medication has or has not had on their sexual activity.

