The schedule and activities of visits will be given to the subject, along with instructions about notification in case of untoward events.

WEEK	0 1	2	3	4	6			3 4 5	6	12	
Pain level (NRS), SAL	X X	X	X	X	X				diary	Mail-in	
History, Exam, MI, pH, Q-tip	X	X		X				—	x		
FSFI, VVSQ, FSD-R	X	X		X	X			x	x	Mail-in	

Patients will be enrolled in the study and randomized to treatment only after all the inclusion and exclusion criteria have been satisfied.

(Visit 1) Week 0

Patients will come to the study clinic to be screened according to the protocol inclusion/exclusion criteria at their first visit prior to randomization into the study. Site personnel must register the patient with the interactive voice response system (IVRS) at this visit to obtain a patient number.

After patients have signed the informed consent, site personnel will review the inclusion and exclusion criteria to ensure that the patient is eligible for the study. The following information will be recorded, or procedures performed for eligible patients. Verbal questioning is to be completed before any invasive procedures are undertaken.

1. Personal and demographic information.
2. Medical/gynecological history including year of last menstrual period to establish post-menopausal state.
3. Drug history (prescription/non-prescription/herbal supplements, including DHEA) for the previous 3 months.
4. Physical examination: The intake pelvic examination, including of the vulva and vagina, will be normal for a woman's age and years since menopause.
5. Vaginal Maturation Index
6. Vaginal pH, bacterial screening swab
7. Q-tip Test to establish localization and rating NRS of vulvar, vestibular pain.
8. Vital signs including blood pressure and heart rate (after sitting 5 minutes) and body temperature, height and weight.
9. Assessment of acute life stress relating to any major life change that interferes with sexual function.
10. Status of patient's sexually functional, both psychologically and physically
11. Establishing that patient is sexually active with self (masturbation) and/ or with partner.
12. During the consent process, all of the questionnaires (including SAL, FSFI, NRS, VVSQ, FSDQ-R) will be reviewed with the patients to allow them to read what they will be expected to complete during their participation in the pre-treatment, treatment and post-treatment periods of the study.

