13. At this visit, the study coordinator or other designated study personnel should read the SAL instructions to the patient and ask her if she has any questions. At the end of the initial visit, each patient will be given instructions that they will receive an email in order to fill out questionnaires online at the end of week 1 (one) , and week 3 (three) to be completed at home, at the end of Day 7 of those weeks, during the treatment period. They will receive a final email at the end of week 6 with instructions to fill out questionnaires anonymously online.

14. All questionnaires, both in clinic and at home, should be completed by each patient, on her own, in a private place. The patient will turn in the completed questionnaires over to the Investigator, with the option of inserting the questionnaire into an envelope which will be labeled with the patient number, name of the questionnaire and visit number. This will be done to enhance the confidentiality of questionnaires for the patient. The Investigator will fax the documents to the Sponsor via the IRIS Imaging System. Originals will be retained at the site. Alternatively, the subject may fill out the questionnaires on the secure, HIPAA compliant, website.
15. The vaginal pH, pH should indicate non-estrogenized vaginal epithelium according to the state criteria. bacterial screen results must be reviewed, signed, and dated by the Investigator prior to dispensing the study medication.

Patients will be enrolled in the study and randomized to treatment only after all the inclusion and exclusion criteria have been satisfied.

At the end of Visit 1, Week 0, site personnel will obtain investigational medication from IVRS and patients will receive a 2-week, 15 gram, supply of the investigational drug or the placebo (“the ointment”). They will be instructed on how to apply “the ointment”. They will be given written instructions on how to apply the ointment.

Instruction Sheet for Use of “The Ointment”:

- Use “the ointment” only on the area affected exactly as indicated by your clinical trial gynecologist.
- Wash your hands before and after application of the ointment. A small amount ½ inch of the ointment should be applied to the affected area using your finger(s), dabbing it on to ensure complete coverage and leaving a thin layer of the ointment as directed by your clinical trial gynecologist.

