The study medication and placebo have a red brown color and may therefore stain underwear. Subjects will be advised to wear panty liners every day that they apply the study medication in order to avoid staining of their underwear with the medication or placebo.

7. Monitoring and Reporting of Adverse Events/Serious Adverse Events: During the study, if you experience any medical problems, suffer a research-related injury, or have questions, concerns or complaints about the study, please contact your clinical trial gynecologist. If you seek emergency care, or hospitalization is required, alert the treating physician that you are participating in a research study being conducted by your clinical trial gynecologist.

Monitoring of Adverse Events will be done by patients reporting any adverse event to their clinical trial gynecologist. No serious adverse events are expected.

8. Study Oversight: In the unlikely event of the need to prematurely terminate this study of 10% , [name] will be the one to decide to terminate the study. The study will be made available for monitoring, auditing, IRB review and regulatory inspection by providing direct access to study related source data.

9. Data Management- Preliminary Power Analyses and Sample Size Estimates

Power Analyses

For Primary Outcome: Pain Score:

Sample size was calculated to achieve at least 80% power with a significance level of 0.05 using a two-tailed, two-sample t test. A sample size of 56 subjects (28 subjects in treatment group and 28 subjects in the placebo group) was estimated to achieve 80% power to detect at least 2.0-points mean difference between treatment and placebo groups. The Initiative on Methods, Measurement, and Pain Assessment in Clinical Trials suggests that reductions in pain intensity of at least 15–20%, or 2 points in the 0–10 scale, reflect clinically important changes (Dvorkin et al, Core Outcome Measures for Chronic Pain Clinical Trials:

IMMPACT Recommendations Pain: 2005 Jan; 113 (1-2) pp: 9-19)). The pain classification on a 0-10 scale will be as follows: 0 no pain; 1-3 mild pain; 4-6 moderate pain; 7-9 significant pain; 10 severe pain. To compensate for possible withdrawal of 15% of patients in the vulvodynia study, a total sample size of 64 participants (32 in the treatment group, 32 in the placebo group) will be required.

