The power analyses were based on previous research data on the effectiveness of the off label use of dilute Veregen (5% sinecatechins ointment) green tea extract (GTE) for the treatment of significant to severe vulvar pain (Patent US 2016/0271102 A1).

Statistical Analyses

Participants randomized to the dilute Veregen (10% sinecatechins ointment) green tea extract (GTE) arm will be compared to those randomized to placebo arm on demographic, descriptive and clinical variables at baseline using chi-square analysis for categorical variables, Student t test and ANOVA test for parametric data and Mann-Whitney U test for nonparametric data.

The ordinal variables (scores from the FSFI, Sexual Distress Scale revised, and the Sexual Activity Log questionnaires) will be analyzed using ANOVA test.

The nominal variables (binary categories from the Vulvovaginal Symptom Questionnaire, Erythema presence/absence and the Sexual Activities Log) will be analyzed using chi-square test. The p-values of less than 0.05 will be considered as statistically significant. These measures will be analyzed at the following assessment points (baseline, 2-week visit, 4-week visit, and 6-week follow-up).

10. IRB Review/Ethics/Informed Consent: Please see attached Informed Consent Document submitted.

IRB Review/Ethics/Informed Consent

This study will be conducted in accordance with the ethical principles that have their origin in the Declaration of Helsinki and that are consistent with Good Clinical Practice and applicable regulatory requirements. The study will be conducted in accordance with the regulations of the United States Food and Drug Administration (FDA) as described in 21 CFR 50 and 56 [add 312 for IND studies or 812 for device studies], applicable laws and the IRB requirements.

The Sponsor will submit any change to the protocol to the IRB for review and approval before implementation. A protocol change intended to eliminate an apparent immediate hazard to subjects will be implemented immediately provided the FDA and the reviewing IRB are notified within 10 working days.

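### Pain and SAL are collected at weeks 1 and 3 but neither week is an analysis point, and no method links a woman's visits although 15% withdrawal is expected

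*Combined protocol and SAP*

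**What the plan says.** **Collection.** Section 1 (Study Related Procedures) says "the subjects will be asked to keep a weekly diary documenting their pain" on the 0-10 NRS, and to complete the SAL. In the schedule table of Section 5, the row "Pain level (NRS), SAL" carries six marks, matching weeks 0, 1, 2, 3, 4 and 6. The table is partly broken in the text, but item 13 of the Week 0 visit confirms that women "fill out questionnaires online at the end of week 1 (one) , and week 3 (three) to be completed at home". Treatment lasts four weeks.

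**Analysis.** Section 9 (Statistical Analyses) deals with the scale scores in one sentence: "The ordinal variables (scores from the FSFI, Sexual Distress Scale revised, and the Sexual Activity Log questionnaires) will be analyzed using ANOVA test". Yes/no items, namely symptom categories, erythema and some SAL entries, are assigned to chi-square. The section then gives the time points: "These measures will be analyzed at the following assessment points (baseline, 2-week visit, 4-week visit, and 6-week follow-up". The measures named just before that sentence do not include pain. Pain is the primary outcome in the Power Analyses, where its only test is the two-sample t test used for sizing.

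**Withdrawal.** The only provision is to raise the sample from 56 to 64: "To compensate for possible withdrawal of 15% of patients in the vulvodynia study". No analysis population, missing-data rule, baseline adjustment or repeated-measures structure is stated.

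**The concern.** Weeks 1 and 3 are asked of every woman and then given no role. The named methods can be applied to repeated scores in two ways, and both have a problem.

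- **Per visit.** A woman who leaves before week 4 contributes nothing to the week-4 comparison, even if she gave ratings at weeks 1 to 3. If leaving depends on pain, and does so differently in the two arms, the women who remain are no longer comparable.
- **Pooled over visits.** Ordinary ANOVA or chi-square treats several values from one woman as independent, so standard errors are wrong.

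Different dropout by arm is possible here. The instruction sheet tells women to stop and report if irritation occurs, and Section 5 provides for women leaving because of it. At stake are possible bias in a week-4 comparison and some precision.

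**Working it through.** **1. Records without a planned use.** The on-treatment weekly points are weeks 1, 2, 3 and 4. Weeks 1 and 3 are not analysis points: 2/4 = 50%, or 2/5 = 40% of post-baseline points if week 6 is counted. This applies to SAL and the self-rated NRS only; FSFI, the symptom questionnaire and the distress scale are not scheduled at weeks 1 and 3.

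**2. The plan's sample size.** Inputs from Section 9: difference 2.0, two-sided 0.05, 80% power, 28 per arm. No SD is stated. Solving the t-test power equation for the SD gives 2.62, which is assumed below. For withdrawal, 56/0.85 = 65.9 and 56 × 1.15 = 64.4, against a stated 64; that is close enough and not at issue. With 15% lost, 32 × 0.85 = 27.2 per arm remain, with power 78.8% at SD 2.62.

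**3. Power recovered at week 4.** Assume equal correlation ρ between weekly scores (not stated in the plan). With k earlier scores from each withdrawn woman:

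R² = kρ² / (1 + (k−1)ρ), and effective n per arm = 1 / [(1−R²)/27.2 + R²/32].

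Example, ρ = 0.5, k = 3: R² = 0.75/2 = 0.375, so n = 1/(0.625/27.2 + 0.375/32) = 28.8.

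| ρ | Week 1 only: n per arm, power | Weeks 1-3: n per arm, power |
|---|---|---|
| 0.3 | 27.6, 79.4% | 27.9, 79.9% |
| 0.5 | 28.3, 80.4% | 28.8, 81.2% |
| 0.7 | 29.4, 81.9% | 30.0, 82.7% |
| 0.8 | 30.1, 82.8% | 30.6, 83.5% |

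Against 78.8%, the gain is about 0.5 to 5 points.

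**4. Precision lost by omitting weeks 1 and 3.** The variance of a k-week mean is SD²(1 + (k−1)ρ)/k. At ρ = 0.5 the factor is 0.75 for weeks 2 and 4, and 0.625 for weeks 1 to 4. The saving is 1 − 0.625/0.75 = 17%. It is 27% at ρ = 0.3, 9% at 0.7 and 6% at 0.8.

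**5. Possible bias at week 4.** Simulation with a true week-4 difference of 2.0 (effect building 0.5, 1, 1.5, 2.0 over weeks 1 to 4), SD 2.62, ρ 0.5 and 0.7, 32 per arm and about 16% dropout driven by the last observed pain score:

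| Dependence of dropout on pain | Completers only | Likelihood, weeks 1-4 |
|---|---|---|
| Equal in both arms | 1.94-1.99 | 1.98-2.03 |
| Active arm only, weak (logit slope 0.1-0.2 per NRS point) | 2.05-2.16 | not reported |
| Active arm only, strong | 2.27-2.40 | 1.95-2.00 |

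The strong case overstates the difference by 0.27/2.0 = 14% to 0.40/2.0 = 20%. A logit slope of about 0.5 per NRS point (odds ratio 1.65) is needed to approach it: that slope gives 2.26-2.35.

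**The case against.** Several stronger readings are tempting, and the documents do not support them.

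- **That all early data from withdrawn women are unused.** Week 2 is an analysis point, so a woman who leaves after that visit still counts at baseline and week 2. What can be lost is her contribution to week 4.
- **That the plan commits to per-visit tests in attenders.** This is the natural reading of the sentence on assessment points, but it is an inference. The type of ANOVA and the analysis population are simply not stated. Inflating a sample for withdrawal is routine and does not itself exclude anyone.
- **That the primary pain result will be overstated by 14-20%.** The plan states no post-baseline pain analysis at all, so this describes a test it might run. The figure also needs strong pain-dependent dropout in one arm only.
- **That irritation is the main expected effect of the study ointment.** Section 6 ties irritation mainly to the full-strength regimen and describes the study regimen as soothing. The documents allow for leaving because of irritation but give no rate.
- **That omitting weekly SAL data costs the equivalent of 1.6 times the sample.** At ρ = 0.5, 4/(1 + 3 × 0.5) = 1.6 compares four weeks with one. The plan already uses weeks 2 and 4, so the relevant ratio is 0.75/0.625 = 1.2.

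Two technical objections also stand. The simulated dropout depends on observed pain, which favours the likelihood model by construction; leaving for irritation need not follow the NRS. And the power gain is small. Neither objection gives weeks 1 and 3 a use or supplies a method for repeated values.

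**Conclusion.** The point holds in limited form. Two of the four on-treatment weekly NRS and SAL records have no planned use, and the plan names no method that links a woman's visits, despite expecting 15% withdrawal. These are facts of the text.

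The consequences are conditional. They depend on whether the tests are run per visit or pooled, and on assumed values for the SD and correlation, neither of which the plan states. On those assumptions the precision gain is modest, and half the records is much less than half the information. The better reasons to act are protection against unequal, pain-related dropout and having one rule fixed in advance. That matters most for pain, which has no stated post-baseline analysis. This is an inexpensive improvement that should be made; it does not show that the planned results would be wrong.

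**What to change.** For the pain NRS and the continuous scale scores, including SAL scores, prespecify a likelihood-based mixed model for repeated measures:

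- **Population:** all randomised women with any post-baseline value.
- **Terms:** arm, week, arm-by-week and baseline value, with unstructured within-woman covariance.
- **Weeks:** 1 to 4 for self-rated NRS and SAL; 2 and 4 for Q-tip NRS and the clinic scales.
- **Result:** the arm contrast at week 4.

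Do not replace the week-4 SAL contrast with a weeks 1-4 total. A total is undefined when weeks are missing, and it can lose power if the effect builds. If SAL followed the simulated pattern, the mean effect would be (0.5 + 1 + 1.5 + 2.0)/4 = 1.25, and efficiency relative to week 4 alone would be (1.25/2.0)² × 1.6 = 0.63 at ρ = 0.5.

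The cost is SAP wording and modest programming, with no new data. The downside is reliance on missing-at-random: the model corrects for dropout explained by recorded scores, not for dropout driven by something unrecorded.
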